7.2 PARTICIPANT DISCONTINUATION/WITHDRAWAL FROM THE STUDY

- Participants may exit the study at any time and for any reason.
- The investigator can temporarily or permanently withdraw a participant from the study for any safety reason or if it is in the participant's best interests.

If a participant withdraws consent, any data collected prior to the date of premature exit may still be used.

Participants are free to withdraw from participation in the study at any time upon request. The patient should be considered to have withdrawn consent only when the patient has withdrawn consent to further participate in any aspect of the study, including any further visits, assessments, or study-related contacts. If a patient fully withdraws consent, the investigator must make every effort to determine the primary reason for this decision and record this information. The study intervention must be discontinued and no further assessments conducted. Information collected prior to withdrawal from the study will still be used. Information that has already been sent to the study Sponsor cannot be withdrawn. All biological material that has not been analyzed at the time of withdrawal must not be used. If the participant requests, previously retained samples will be destroyed to prevent further analysis. Further attempts to contact the patient are not allowed unless safety findings require communicating or follow-up. However, if local regulations permit, the investigator will be asked to check public registries on a regular basis to obtain the survival status (dead or alive) of any patients who failed to complete the study.

In case of serious adverse events, see the corresponding section 8.3.6 for reporting requirements.

If a participant discontinues the study, this will in no way affect their usual care for their condition. In the event of serious adverse events following premature discontinuation of treatment see section 7.1.

Patients who are randomized in error may be withdrawn from the study and replaced (with assignment of new study identification number and new randomization). Patients randomized in error will not be included in the analyses.

Patients who are randomized and then withdraw or are withdrawn from the study will not be replaced. These patients will be included in analyses. Incomplete follow-up will be handled as censored observations in time-to-event analyses, and missing data will be handled through imputation as appropriate.

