3 OBJECTIVES AND ENDPOINTS

OBJECTIVES	ENDPOINTS	JUSTIFICATION FOR ENDPOINTS
Primary		
To assess the effects of prednisone therapy started in the ED and continued for up to 7 days on the change of CRP level	Change in CRP level at 7 days	CRP levels increase rapidly in response to trauma, inflammation and infection and decrease rapidly with resolution of these conditions (Du Clos 2000). Thus, CRP measurement is widely used to monitor inflammatory states.
Secondary		
To compare the effects on the occurrence of death, hospital readmission for HF or worsening HF (WHF) through day 91	The composite of first event of a WHF adverse event, hospital readmission for HF, or death through day 91	WHF has been shown to be associated with longer hospital stay and increased risk of HF readmission and death, and HF readmission and death are outcomes representing disease progression. The composite is a generally accepted endpoint in AHF trials. For this pilot study, the definition of WHF has been expanded to include all reported adverse events of WHF (not only those requiring intensification of IV therapy or mechanical support) over a broader timeframe (longer than 7 days).
To compare the effects on change in quality of life (QoL) as measured by the EQ-5D-5L questionnaire at day 7	Changes in quality of life measured by the EQ-5D-5L from randomization to day 7	Quality of life, encompassing functional capacity, psychological status, and frequent rehospitalizations may be particularly important to patients (Nieminen, Dickstein et al. 2015) The EQ-5D is a validated, standardized instrument developed by EuroQol.
Tertiary/Exploratory		

OBJECTIVES	ENDPOINTS	JUSTIFICATION FOR ENDPOINTS
To compare the effects on the occurrence of death, hospital readmission for HF or worsening HF (WHF) through day 31	The composite of WHF, death, or hospital readmission for decompensated HF at day 31. WHF is defined as worsening signs and/or symptoms of HF that require an intensification of intravenous therapy (including initiation or re-initiation or dose increase) for HF or mechanical ventilatory, renal or circulatory support (occurring between 24 hours after randomization and the earlier of discharge or day 7).	WHF has been shown to be associated with longer hospital stay and increased risk of HF readmission and death, and HF readmission and death are outcomes representing disease progression. The composite is a generally accepted endpoint in AHF trials.

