7 STUDY INTERVENTION DISCONTINUATION AND PARTICIPANT DISCONTINUATION/WITHDRAWAL

7.1 DISCONTINUATION OF STUDY INTERVENTION

Several situations are possible:

- Temporary suspension of treatment: the investigator must document the reason for suspending and resuming the treatment in the participant's source file and the case report form (CRF)
- Premature discontinuation of treatment, but the participant remains enrolled in the study until the end of their participation
- Premature discontinuation of treatment and withdrawal from the study
- If, during the course of his/her participation in the study, the participant presents one of the following criteria, then the study treatment must be discontinued but the participant will continue to be monitored for the study.
 - Thrombo-embolism event
 - Fracture
 - Gastro-intestinal bleeding
 - altered consciousness, confusion or dementia, psychotic state,
 - vaccination, hypersensitivity reaction,
 - pregnancy, severe renal or hepatic impairment, or
 - uncontrolled hyperglycemia.

The investigator must:

- Document the reason(s)
- Collect the assessment criteria at the time of ending participation in the study, if the participant agrees
- Schedule a follow-up for the participant, particularly in case of a serious adverse event.

In the case of severe adverse events, the investigator must notify the sponsor and follow up the participant for 1 month following the premature discontinuation of treatment. The Sponsor will be notified immediately of any serious adverse event. The serious adverse event will be monitored until it is resolved.

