8.3.7 Events of Special Interest

As done in usual care, any secondary effect of steroids treatment will be assessed at every visit with a special attention to:

- Active infection
- Thrombo-embolism event
- Fracture
- Gastro-intestinal bleeding

The investigator must notify the sponsor without delay on the day the investigator becomes aware of the following adverse events, in the same manner and within the same deadline as for serious adverse events (see above).

- Thrombo-embolic event
- Gastro-intestinal bleeding

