10.1.2 Study Discontinuation and Closure

The Sponsor can prematurely discontinue all or part of the study, temporarily or permanently, further to the recommendations of the Medical Monitor if suspected unexpected serious adverse reactions (SUSARs) are observed in one of the treatment arms or if there is a discrepancy in the serious adverse reactions between the treatment arms, requiring a reassessment of the benefit-risk ratio for the study.

Similarly, the Sponsor or the Competent Authority may decide to prematurely discontinue the study due to unforeseen issues or new information about the product, in light of which the objectives of the study or clinical program are unlikely to be achieved.

The Sponsor reserves the right to permanently suspend enrolment at any time if it appears that the inclusion objectives are not met.

Patients already enrolled in the study at the time the study is prematurely discontinued will complete all study assessments through Day 91 as set forth in the protocol.

If the study is prematurely discontinued for safety reasons, the decision and justification will be provided by the sponsor to the Competent Authority and to the Ethics Committees within a period of 15 days.

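### Section 7.2 lets an unblinded investigator take a participant out of the whole study for safety, so day-7 CRP can be lost informatively, most plausibly after infection

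*Protocol*

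**What the plan says.** Section 7.2 treats two kinds of exit separately. Consent withdrawal is defined narrowly, as refusal of every further aspect of the study. Independently of that, "The investigator can temporarily or permanently withdraw a participant from the study for any safety reason", or in the participant's best interests.

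Section 7.1 lists several possible situations side by side. One is "Premature discontinuation of treatment, but the participant remains enrolled in the study until the end of their participation". Another is "Premature discontinuation of treatment and withdrawal from the study". Neither is named as the default. For a set of named events (among them thrombo-embolism, fracture, gastro-intestinal bleeding, confusion and uncontrolled hyperglycemia), "then the study treatment must be discontinued but the participant will continue to be monitored for the study". Infection is not named.

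Section 8.3.7 says that "any secondary effect of steroids treatment will be assessed at every visit with a special attention to" four events, and active infection comes first. The other three are all on the 7.1 list. Section 3 justifies the primary endpoint by noting that "CRP levels increase rapidly in response to trauma, inflammation and infection and decrease rapidly with resolution of these conditions".

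There are partial safeguards. Section 7.1 asks for assessments at exit if the participant agrees, and after severe adverse events the investigator must "follow up the participant for 1 month following the premature discontinuation of treatment". Section 8.1.6 seeks vital status for everyone randomized. None of these names a day-7 CRP sample.

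If the sponsor stops the whole trial early, section 10.1.2 is stricter: patients already enrolled "will complete all study assessments through Day 91 as set forth in the protocol".

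**The concern.** Stopping a drug and leaving a study are different things, and 7.2 lets one safety decision do both. The investigator knows the allocation, and only the prednisone arm has a study drug to blame, so such withdrawals may be more common in that arm. Unequal loss is a risk that the rule permits; the protocol does not say that it will happen.

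Infection is the case where the direction of bias can be argued from the protocol itself: it is a steroid effect of interest and it raises the primary outcome. If infected prednisone patients leave before day 7, high CRP values leave that arm and the comparison moves in favour of prednisone. For other safety reasons the direction is not established.

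The analysis treats these losses as uninformative. Section 9.4.2 fits a mixed model for repeated measures (MMRM) to available CRP values without imputation, and 9.4.3 censors the composite at last available follow-up. Day-7 EQ-5D, heart failure readmission to day 91, and new non-serious adverse events and worsening heart failure to day 31 are also exposed. Deaths are largely protected by the vital-status effort, and a patient withdrawn because of a worsening heart failure adverse event already counts in the composite.

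**Working it through.** **Inputs from the protocol (9.2).** 60 patients per arm, SD of log CRP 1.002, two-sided alpha 0.05, target ratio 0.60 (log difference 0.511), stated power about 80%.

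**The plan's own figure.** A two-sample t-test with these inputs has 79.1% power, so the stated figure reproduces. Losing 3 or 6 prednisone patients lowers it only to 78.0% or 76.9%. The issue is bias, not power.

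**Assumed inputs.** The protocol gives no withdrawal or infection rate. Let kp and kc be the prednisone and control patients lost before day 7, and let d be the excess of their day-7 log CRP over the retained patients, in SDs. The ranges used are kp = 3 to 6, kc = 0 to 2, d = 0.5 to 1.

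**Bias in a comparison of patients with a day-7 value.** Dropping k of 60 patients whose mean lies d SDs above the rest lowers the arm mean by (k/60) × d × 1.002. Hence:

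- bias in the log ratio = −((kp − kc)/60) × d × 1.002
- SE = 1.002 × √(1/(60 − kp) + 1/(60 − kc))
- type I error (normal approximation) = Φ(−1.96 + |bias|/SE) + Φ(−1.96 − |bias|/SE)

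With a true ratio of 1.00:

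| kp | kc | d | Bias (log) | Apparent ratio | SE | Bias/SE | Type I error |
|---|---|---|---|---|---|---|---|
| 3 | 0 | 0.5 | −0.025 | 0.975 | 0.185 | 0.14 | 5.2% |
| 3 | 0 | 1 | −0.050 | 0.951 | 0.185 | 0.27 | 5.8% |
| 6 | 0 | 0.5 | −0.050 | 0.951 | 0.188 | 0.27 | 5.8% |
| 6 | 0 | 1 | −0.100 | 0.905 | 0.188 | 0.53 | 8.3% |
| 3 | 1 | 0.5 | −0.017 | 0.983 | 0.186 | 0.09 | 5.1% |
| 6 | 2 | 1 | −0.067 | 0.935 | 0.189 | 0.35 | 6.4% |
| equal | equal | any | 0 | 1.000 | – | 0 | 5.0% |

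**What the MMRM recovers.** The model borrows from day 2 and day 4. With first-order autoregressive residuals, day 4–day 7 correlation ρ, and a fraction f of the excess already visible at day 4, the remaining bias is about (1 − ρf) times the figure above. Taking ρ = 0.5 as an assumption:

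- f = 1: half remains. The extremes become exp(−0.0125) = 0.99 and exp(−0.050) = 0.95 with losses in one arm, and 0.99 and 0.97 with losses in both.
- f = 0.5: three quarters remains, giving 0.98 and 0.93 with losses in one arm.
- f = 0 (infection appears after day 4): nothing is recovered.

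Simulation with 6,000 runs per setting agrees within simulation error.

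**Composite endpoint.** Not quantified, because deaths and worsening heart failure before withdrawal are still captured.

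**The case against.** The strongest reply is that the omission of infection is being misread. The 7.1 list names events that force the drug to stop, and monitoring is the safeguard attached to that stop. An infected patient need not stop at all and can attend the day-7 visit like anyone else. Leaving the study takes a further discretionary step. That is right, and it means that loss is permitted and not inevitable. It does not remove the permission, which 7.2 grants without limit.

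Second, an infection serious enough to prompt withdrawal will often count as severe, so the one-month follow-up applies and runs past day 7. This helps the safety record. It does not secure a CRP sample.

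Third, a patient who stops prednisone early may be excluded from the per-protocol main analysis (9.3) as not having followed the allocated treatment. If so, keeping the sample does not change the main result. This stands as a limit on the finding. In that case, though, the intention-to-treat (ITT) sensitivity analysis is the check on those exclusions, and it needs the day-7 values.

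Fourth, the size is assumed and small against a design ratio of 0.60, and index events triggered by infection are already excluded at entry. Both points are accepted.

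Fifth, missing-data sensitivity analyses belong in the statistical analysis plan. They do, but no analysis recovers a sample that was never drawn.

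Finally, narrowing the clause might seem to remove protection for a patient who becomes confused. Confusion is already on the 7.1 list, where monitoring continues, and the proposed wording takes blood only where safe and agreed.

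**Conclusion.** The concern holds. The protocol lets an unblinded investigator end a participant's whole study involvement on safety grounds without withdrawal of consent, and no other text guarantees the day-7 CRP afterwards.

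Under the assumed range, an apparent ratio of 0.98 to 0.90 under the null (0.14 to 0.53 standard errors) is the span if only prednisone patients are lost and nothing is recovered from earlier visits. It is 0.98 to 0.94 if some controls are lost too. The 8.3% type I error is the extreme corner. Equal losses give no bias.

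The direction, towards prednisone, is supported for infection only. The effect bears on the ITT sensitivity analysis. It bears on the per-protocol main analysis only if safety stops are not classed as a treatment violation. This is a modest, avoidable weakness that should be corrected, and it does not undermine the design.

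**What to change.** In 7.2, replace the bullet on investigator withdrawal with wording such as:

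> For safety reasons, or in the participant's best interests, the investigator discontinues study treatment only. The participant stays in scheduled follow-up through day 91, including the day-7 CRP sample where the participant agrees and it is safe, and in adverse event recording for the same period as all participants, unless consent is withdrawn. If a hospital visit is not possible, the other outcomes are collected by telephone or from records.

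In 7.1, limit the situation that combines stopping treatment with leaving the study to withdrawal of consent. The rule for patients randomized in error stays as it is. Infection need not be added to the 7.1 list, which would make every infection a compulsory stop.

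**Cost.** The wording changes are short, but they need a protocol amendment with sponsor agreement and ethics approval. No visits are added, since all are already scheduled for every patient. Sites would have to pursue follow-up in a few patients they would otherwise have withdrawn.

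**Limit.** Where a blood draw is unsafe or refused, day-7 CRP is still lost.

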7.3 LOST TO FOLLOW-UP

If the participant cannot be located, the investigator must make every effort to reconnect with the participant (and document his attempts in the source file), at least to determine whether the participant is alive or dead.

8 STUDY ASSESSMENTS AND PROCEDURES

8.1 EFFICACY ASSESSMENTS

8.1.1 C-reactive protein

C-reactive protein will be measured at 24 hours, 72 hours, and day 7.

8.1.2 Physical examination

A study physician will perform a physical examination including vital signs, weight, and a clinical HF assessment at Visits 1 (randomization), Visit 2 (24 hours' post-randomization (day 2)), Visit 3 (72 hours post-randomization (day 4)) or at discharge if earlier, Visit 4 (day 7), and Visit 5 (30 days post-randomization). To reduce variability and increase sensitivity to detect changes, these evaluations should be done at the same time of day if possible, in the same position(s), and, preferably, in the same setting and by the same assessor.

Vital signs will include temperature, pulse, respiratory rate, systolic and diastolic blood pressure and weight. Height will be measured at Visit 1. Vital signs recorded as part of routine standard of care during the admission and prior to inclusion are considered part of the medical history required to assess study eligibility. Systolic and diastolic blood pressure should be measured during follow up visits using an appropriately sized blood pressure cuff in both arms at least once, and the arm with the higher blood pressure used for all subsequent measurements. To reduce variability, body weight should be measured using the same scale throughout if possible.

The clinical HF assessment will include ratings of the following HF signs and symptoms:

Dyspnea on exertion / NYHA class:

Class I: No limitation of physical activity. Ordinary physical activity does not cause undue fatigue, palpitation, dyspnea (shortness of breath).

Class II: Slight limitation of physical activity. Comfortable at rest. Ordinary physical activity results in fatigue, palpitation, dyspnea (shortness of breath).

Class III: Marked limitation of physical activity. Comfortable at rest. Less than ordinary activity causes fatigue, palpitation, or dyspnea.

Class IV: Unable to carry on any physical activity without discomfort. Symptoms of heart failure at rest. If any physical activity is undertaken, discomfort increases.

Orthopnea: Patient should be observed after being in the lowest recumbent position for 10 – 15 minutes or queried to determine the minimum number of “pillows” required to obtain/maintain comfort while supine:

0 = None

1 = 1 pillow (10 cm)

2 = 2 pillows (20 cm)

3 = > 30 degrees

Not evaluable: Examination could not be performed / result unobtainable. The patient is on mechanical ventilation for non-cardiac reasons, cannot lie flat due to body habitus or orthopedic restrictions.

Peripheral Edema: edema in any dependent area, including the lower extremities or the sacral region.

0: Complete absence of skin indentation with mild digital pressure in all dependent areas.

1+: Indentation of skin that resolves over 10–15 seconds.

2+: Indentation of skin is easily created with limited pressure and disappears slowly (15–30 seconds or more).

3+: Large areas of indentation easily produced and slow to resolve (> 30 seconds).

Rales:

No rales: No rales after clearing with cough.

Rales < 1/3: Moist or dry rales heard in lower 1/3 of one or both lung fields that persist after cough.

Rales 1/3–2/3: Moist or dry rales heard throughout the lower half to 2/3 of one or both lung fields.

Rales > 2/3: Moist or dry rales heard throughout both lung fields.

Jugular venous pulse (JVP) in centimeters as 5 + (the vertical distance from the top of the pulsation in jugular veins to the sternal angle of Louis). Assess with patient supine at ~ 45° off the horizontal until the jugular venous pulsation is visible half-way up the neck.

< 6 cm: Complete absence of discernable venous wave, even with hepatic compression.

6–10 cm: Venous wave detectable during expiration or complete respiratory cycle, less than 4 cm above clavicle (< 10 cm).

> 10 cm: Presence of venous wave throughout respiratory cycle sometimes \geq 4 cm above clavicle and increased with hepatic compressions.

Not evaluable: Examination could not be performed/result unobtainable. Unable to determine due to patient's body build (habitus) or other reason.

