9.4.9 Exploratory Analyses

The following exploratory endpoints will be assessed:

1. The composite of WHF, death, or hospital readmission for decompensated HF at day 31, where WHF is defined as worsening signs and/or symptoms of HF that require an intensification of intravenous therapy (including initiation or re-initiation or dose increase) for HF or mechanical ventilatory, renal or circulatory support (occurring between 24 hours after randomization and the earlier of discharge or day 7).
2. The composite of WHF, death, or hospital readmission for decompensated HF at day 91, where WHF is defined as worsening signs and/or symptoms of HF that require an intensification of intravenous therapy (including initiation or re-initiation or dose increase) for HF or mechanical ventilatory, renal or circulatory support (occurring between 24 hours after randomization and the earlier of discharge or day 7).
3. Changes in quality of life measured by the EQ-5D-5L from randomization to day 31.
4. Changes from randomization to day 7 in NYHA classification, orthopnea, peripheral edema, rales, jugular venous pulse, and body weight.
5. Death from any cause to days 31 and 91.
6. Readmission for HF or death to days 31 and 91.
7. HF readmission through days 31 and 91.
8. Requirement for treatment with intravenous vasopressors, inotropes, and/or mechanical ventilatory, renal or circulatory support or death from randomization through day 7 (“treatment failure”).
9. Changes from randomization to day 7 and to day 31, in biomarker levels including brain natriuretic peptide (BNP), NT-pro-BNP, creatinine and troponin.
10. Time to worsening heart failure through the earlier of day 7 or discharge.
11. Length of stay in ICU through 30 days following randomization

12. Length of initial hospitalization through 30 days following randomization
13. Days dead or in acute care (including all intensive acute care units) out of the first 30 days following randomization.
14. Days dead or in the hospital out of the first 30 days following randomization.
15. Hospital re-admission through days 31 and 91.

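### Some bedside grades for JVP, edema and rales overlap, leave gaps or contradict their labels, which affects only exploratory day-7 endpoints

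*Protocol*

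**What the plan says.** Section 8.1.2 defines JVP in centimetres as 5 plus "the vertical distance from the top of the pulsation in jugular veins to the sternal angle of Louis". It then gives three categories:

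- Lowest: "< 6 cm: Complete absence of discernable venous wave, even with hepatic compression".
- Middle, labelled 6–10 cm: a wave seen in expiration or through the whole cycle, "less than 4 cm above clavicle (< 10 cm".
- Top: "> 10 cm: Presence of venous wave throughout respiratory cycle sometimes" at least 4 cm above the clavicle.

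Peripheral edema is graded mainly by how long the indentation lasts. Grade 0 is no indentation and 1+ is 10–15 s. Grade 2+ is an easily made indentation that "disappears slowly (15–30 seconds or more". Grade 3+ is more than 30 s over large areas.

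Rales have the labels none, < 1/3, 1/3–2/3 and > 2/3. The 1/3–2/3 grade is described as "Moist or dry rales heard throughout the lower half to 2/3 of one or both lung fields". The > 2/3 grade is described as covering both lung fields completely.

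The grades are used in Section 3 and in Section 9.4.9, item 4: "Changes from randomization to day 7 in NYHA classification, orthopnea, peripheral edema, rales, jugular venous pulse, and body weight". Section 8.1.2 asks for the same time of day if possible, the same position and, preferably, the same setting and assessor. Section 6.3 states that the trial is open-label.

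**The concern.** A graded scale should place each patient in exactly one grade. Here the number, the label and the descriptive text of a grade sometimes point to different grades, or to none. Two physicians can then grade the same patient differently by relying on different parts of the definition. One physician can also grade a patient differently at baseline and day 7. Either way a change could be recorded with no change in the patient.

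The assessors know the allocation. Section 4.2 defends the open-label design on the ground that CRP, rehospitalization and death are objective, and that defence does not extend to bedside signs. An analysis plan cannot repair the ambiguity later. The grades are assigned at the examination, and the protocol does not clearly ask sites to keep the underlying refill time or lung extent.

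**Working it through.** The protocol states no figure to reproduce here. The check sets each label against its description and looks for overlaps, gaps and conflicts.

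**JVP, upper boundary.** Let c be the vertical height of the clavicle above the sternal angle, in cm. The protocol gives no value, so c is an assumption. A pulsation 4 cm above the clavicle is c + 4 cm above the angle. On the protocol's scale this is 5 + c + 4 = 9 + c.

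| Assumed c (cm) | 4 cm above clavicle, on the protocol's scale (cm) | Labelled boundary (cm) |
|---|---|---|
| 0 | 9 | 10 |
| 1 | 10 | 10 |
| 2 | 11 | 10 |
| 3 | 12 | 10 |
| 4 | 13 | 10 |

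The two rules agree only at c = 1. For any other c, values between 10 and 9 + c fall in one category by number and in the other by landmark. The use of two different reference points needs no assumption; the size of the discrepancy does.

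**JVP, exactly 10 cm.** The label 6–10 includes it. The text of that category (below 10) and the top label (above 10) both exclude it.

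**Edema, by time.**

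| Indentation lasts | Grades whose timing is met |
|---|---|
| under 10 s | none (0 requires no indentation) |
| 10 s | 1+ |
| 15 s | 1+ and 2+ |
| 20 s, 30 s | 2+ |
| 31 s, 45 s | 2+ and 3+ |

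Grade 2+ has no upper time limit and sets no limit on area. Grade 3+ adds large areas. A large-area indentation lasting over 30 s therefore satisfies both descriptions.

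**Rales, by extent.**

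| Extent | By label | By description |
|---|---|---|
| 40% or 45% | 1/3–2/3 | none (text starts at one half) |
| 50% or 60% | 1/3–2/3 | 1/3–2/3 |
| 70% or 80% | > 2/3 | none (text requires all of both fields) |
| above 2/3 of one lung only | label does not say which lung counts | none |

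**Where the grades are used.** Section 9.4.9, item 4 lists six separate changes, of which edema, rales and JVP are three. The CRP analysis (Section 9.4.2) and the secondary analyses (Section 9.4.3) do not use the grades. Worsening heart failure (Section 8.1.5) refers to worsening signs but sets no grade threshold.

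**The case against.** The strongest reply is that the JVP text is a bedside approximation with one nominal clavicle height. At c = 1 the clavicle sits at 5 + 1 = 6 cm and 4 cm above it is 10 cm, so both boundaries line up. This stands against a tempting further charge: that a pulsation 0.5 cm above the angle (5.5 cm) contradicts the lowest category, whose text says no wave is seen. At c = 1 that pulsation is below the clavicle and the category can be read as intended. The reply does not cure the main problem, because the protocol never states the nominal height and the measured value uses the patient's own anatomy. It also leaves the conflict at exactly 10 cm. In addition, the top category says only that the wave is sometimes at least 4 cm above the clavicle, so 4 cm is not a firm cut on that side. The 9 + c calculation therefore shows that the landmarks disagree, not how many patients are misgraded.

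On edema, a reader might infer that every indentation over 30 s is ambiguous. It is not: a localized one fits 2+ alone, because 3+ requires large areas. The overlap is limited to large-area edema.

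On rales, a reader might infer that an extent of 40% cannot be graded. The label 1/3–2/3 covers it; only the description leaves it out. Extent above 2/3 in one lung only is the case with no clear answer.

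The standardization in Section 8.1.2 reduces variation, and the Manual of Procedures (mentioned in Section 10.1.10) or the CRF may hold firmer grading rules. Neither is available here. The conditions in Section 8.1.2 are qualified as preferred or where possible, and they do not settle which part of a definition governs.

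**Conclusion.** The point holds as a minor defect of definition. The conflict of JVP reference points, the 10 cm boundary, the edema overlaps at 15 s and (for large areas) above 30 s, and the mismatches between rales labels and descriptions are all in the current text. Only the numerical span of the JVP discrepancy depends on an assumption: 9 to 13 cm against 10 cm for an assumed c of 0–4 cm.

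The consequence is confined to three separate exploratory day-7 changes. A reader might infer that half of a combined sign score is unreliable, but the protocol defines no combined score. Nor do the documents support any effect on CRP, on the clinical composite or on quality of life, or a bias in a known direction. How many patients would be graded differently cannot be derived from the protocol.

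**What to change.** Amend the grading text in Section 8.1.2 and use identical wording on the CRF:

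- **JVP:** grade only on the calculated value from the sternal angle (< 6, 6 to 10 inclusive, > 10 cm) and record the value in cm. State that no visible wave is graded < 6 cm, so that removing the descriptive anchors does not turn those patients into missing data.
- **Edema:** make the time bands exclusive (for example, 2+ ends at 30 s), assign 15 s to one grade, and say where an indentation resolving in under 10 s belongs. Keep the extent wording and state which criterion decides when time and extent disagree.
- **Rales:** let the labels govern, make the descriptions match them, and score the worse lung.

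Apply the new text only to patients randomized after the change, so that each patient's baseline and day 7 are graded under one version. The cost is protocol and CRF wording and a short site memo; eligibility, visits and sample size do not change. The downside is that earlier patients remain graded under the old text, so the date of the change must be documented.
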